2.8.1 Adverse events (AEs)

Summary tables for adverse events (AEs) will include only the **treatment-emergent** AEs i.e. events that started after the first dose of study treatment or events present prior to the first dose of study treatment but increased in severity based on preferred term until 12 weeks after last dose of study treatment.

The treatment-emergent adverse events will be summarized by system organ class and preferred term, severity (mild, moderate, severe), type of adverse event, relation to study treatment. If a patient reported more than one AE with the same preferred term, the AE with the greatest severity will be presented. If a patient reported more than one AE within the same primary system organ class, the patient will be counted only once with the greatest severity at the system organ class level, where applicable.

For the reporting requirements of ClinicalTrials.gov and EudraCT, two required tables on <on-treatment/treatment emergent> adverse events which are not serious adverse events with an incidence greater than 2% and on <on-treatment/treatment emergent> SAEs and SAEs suspected to be related to study treatment will be provided by SOC system organ class and PT preferred term on the safety set population.

If for a same patient, several consecutive AEs (irrespective of study treatment causality, seriousness and severity) occurred with the same SOC and PT:

- a single occurrence will be counted if there is ≤ 1 day gap between the end date of the preceding AE and the start date of the consecutive AE
- more than one occurrence will be counted if there is > 1 day gap between the end date of the preceding AE and the start date of the consecutive AE

For calculating the frequencies, the presence of at least one SAE / SAE suspected to be related to study treatment / non SAE has to be checked in a block e.g., among AE's in a ≤ 1 day gap block, if at least one SAE is occurring, then one occurrence is calculated for that SAE.

The following adverse event summaries will be produced by treatment for Safety Set:

- Adverse events (overall and severe), regardless of study drug relationship by primary system organ class and preferred term
- Adverse events, regardless of study drug relationship by primary system organ class and preferred term and severity
- Adverse events (overall and severe), with suspected study drug relationship by primary system organ class and by preferred term
- Serious adverse events (overall and severe), regardless of study drug relationship, by primary system organ class and preferred term
- Serious adverse events (overall and severe), with suspected study drug relationship, by primary system organ class and preferred term
- Adverse events leading to study drug discontinuation (overall and severe), regardless of study drug relationship, by primary system organ class and preferred term
- Adverse events requiring dose adjustment or study-drug interruption (overall and severe), regardless of study drug relationship, by primary system organ class and preferred term
- Adverse events requiring additional therapy (overall and severe), regardless of study drug relationship, by primary system organ class and preferred term
- Deaths by primary system organ class and preferred term.
- Non-serious adverse events with a frequency greater than 2% regardless of study drug relationship, by primary system organ class and preferred term (for the legal requirements of ClinicalTrials.gov and EudraCT)

The crude rates of treatment-emergent adverse events will be summarized by primary system organ class and preferred term.

In addition, exposure time-adjusted incidence rates including 95% confidence intervals will be provided for the entire treatment period at the preferred term level for all SAEs and the common AEs (defined as with a frequency greater than 2%). A graphical display of the crude rates and exposure-adjusted incidence rates will be presented for all AEs and SAEs by SOC.

Exposure-adjusted AE incidence is defined as:

$(\text{Number of patients with new or worsened treatment emergent AEs}) / (\text{Total number of days a patient is on treatment summed over all patient}/365.25)$

The logic for calculation of the duration on treatment for a patient for exposure- adjusted AE at week x is as follows.

1) For treatment period 1 related reports:

If event occurred till week x: Duration=AE start date- date of first dose on study treatment +1

If event did not occur till week x: Duration= date of week x- date of first dose on study treatment +1

2) For entire treatment period related reports:

Please do not consider the duration when the subject is on placebo.

If event occurred till week x: Duration=AE start date- date of first dose on active study treatment +1

If event did not occur till week x: Duration= date of week x- date of first dose on active study treatment +1.

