Proportion of patients achieving a satisfactory Patient Acceptable Symptom State (PASS) at Week 1, 2, 3, 4 and 8 with secukinumab 150 mg compared to placebo.	Proportion of patients achieving a satisfactory PASS at Week 1, 2, 3, 4 and 8 in Group A compared to Group B.

Proportion of patients in each of treatment arm achieving a satisfactory PASS at Week 12, Week 20 and Week 24.	Proportion of patients achieving a satisfactory PASS at Week 12, Week 20 and Week 24 in Arm A1, Arm A2 vs Arm A3, and Arm B1 vs Arm B2.
Spinal pain NRS score according to previous exposure to tumor necrosis factor (TNF) inhibitors at Week 1, 2, 3, 4, 8, 12 and 24	Proportion of patients achieving a spinal pain score < 4 for TNF-naïve patients compared to TNF α -IR patients at Week 1, 2,3, 4, 8, 12 and Week 24
Proportion of patients who responded to secukinumab 150 mg at Week 8 (i.e. spinal pain score < 4 on a 0-10 NRS) maintaining a response at Week 24.	Proportion of patients with spinal pain score < 4 on a 0-10 NRS at Week 8 maintaining a spinal pain score < 4 at Week 24.
Proportion of patients achieving an improvement in ASAS health index with secukinumab 150 mg compared to placebo at Week 8.	Proportion of patients achieving an improvement in ASAS health index with secukinumab 150 mg compared to placebo at Week 8.
Proportion of patients achieving an improvement in ASAS health index in each treatment arm at Week 24.	Proportion of patients achieving an improvement in ASAS health index in each treatment arm at Week 24.
ASAS health index at Week 8 and Week 24.	Mean ASAS health index score in each treatment arm at Week 8 and Week 24
Change from baseline in total spinal pain NRS score at all time points.	Total spinal pain NRS score in each treatment arm at all time points.
Change from baseline in total BASDAI score at all time points.	Total BASDAI score in each treatment arm at all time points.
ASDAS-CRP at Week 8 and Week 24.	Mean ASDAS-CRP in each treatment arm at Week 8 and Week 24.
[REDACTED]	
[REDACTED]	
Safety and tolerability of secukinumab 150 mg and 300 mg over the study period.	Safety and tolerability, as measured by frequency and severity of adverse events and changes in laboratory values of interest for secukinumab 150 mg and placebo (Baseline to Week 8) and for secukinumab 150 mg and 300 mg (Week 8 to Week 24).

2 Statistical methods

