2.4 Treatments (study treatment, rescue medication, concomitant therapies, compliance)

2.4.1 Study treatment / compliance

Study Treatment

The summaries by treatment will be performed by the actual treatment received (as follows) for each treatment period.

Treatment group for period I:

- Group A: AIN457 150 mg
- Group B: Placebo

Treatment group for period II:

- Arm A1: AIN457 150 mg
- Arm A2: AIN457 150 mg
- Arm A3: AIN457 300 mg
- Arm B1: AIN457 150 mg
- Arm B2: AIN457 300 mg

The analysis of study treatment data will be based on the safety set for period I, period II and the entire treatment period separately. The number of active and placebo injections will be summarized by treatment group up to Week 8, the number of double blind injections will be summarized by treatment group from Week 8 to Week 24.

Rescue medication

Not applicable.

Duration of exposure

The duration of exposure to study treatment will be summarized by treatment group. In addition, the number and percentage of patients with cumulative exposure levels (e.g. any exposure, ≥ 1 week, ≥ 2 weeks, ≥ 3 weeks, ≥ 4 weeks, ≥ 8 weeks, etc.) will be presented.

Duration of exposure for secukinumab groups will be defined as the time from first dose of study treatment to the time of treatment end for each treatment period. Duration of exposure for the placebo group will be defined as the time from first dose of placebo treatment to the time of treatment end in treatment period 1 and the time from first dose of active treatment to the time of treatment end in treatment period 2.

For patients who discontinue, this will be the patient's last visit in the corresponding treatment period.

Duration of exposure (years) = duration of exposure (days) / 365.25

Duration of exposure (100 subject years) = duration of exposure (years) / 100

The analyses of duration of exposure described above will be done for both the study treatment periods.

Compliance

Compliance will be calculated based on documented study drug administrations and syringe counts and displayed by treatment group.

Compliance is expected to be 100%, unless temporary interruption is needed for safety reasons. Compliance will also be assessed by a Novartis monitor using information provided by the authorized site personnel.

Compliance (%) = 100(total no of injections administered)/(no. of injections prescribed).*

Compliance for entire treatment period will be based on active treatment exposure.

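### The exposure-adjusted AE rates start at the first active dose and have no Treatment Period 2 version, so the 300 mg versus 150 mg contrast in Arms A3 and A2 is diluted by eight shared weeks on 150 mg

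*SAP*

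**What the plan says.** SAP 2.8.1 plans crude rates of treatment-emergent events and, in addition, for SAEs and common AEs, that "exposure time-adjusted incidence rates including 95% confidence intervals will be provided for the entire treatment period at the preferred term level". SAP 2.8.1.1 repeats this for AEs of special interest and gives differences in exposure as the reason. The rate is the number of patients with an event divided by total time on treatment in years.

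Two duration rules follow. The first, "1) For treatment period 1 related reports", counts from the first dose of study treatment. The second, "2) For entire treatment period related reports", carries the instruction "Please do not consider the duration when the subject is on placebo". It then counts from the first active dose: with an event, "Duration=AE start date- date of first dose on active study treatment +1"; without one, "Duration= date of week x- date of first dose on active study treatment +1". There is no third rule for Weeks 8 to 24.

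The surrounding text matters too:
- SAP 1.1: Group A takes 150 mg from Baseline. Group B takes its first active dose at Week 8.
- SAP 2.1 and 2.8: Period 2 is presented by the five arms, and safety is summarised separately for Period 1 and Period 2.
- SAP 2.4.1: the Period 2 groups include "Arm A3: AIN457 300 mg".
- SAP Table 1.2-1: the safety endpoint covers frequency and severity of AEs and laboratory changes, among others "for secukinumab 150 mg and 300 mg (Week 8 to Week 24"). Protocol 1.2 names the same dose comparison over the same weeks as a purpose of the study.

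**The concern.** A2 and A3 are the randomised test of staying on 150 mg against moving to 300 mg among Week 8 non-responders. Before Week 8 both arms received the same 150 mg regimen, so those weeks carry no information on the dose contrast. Under the entire-period rule they still enter numerator and denominator of both arms.

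The clock also stops at the first event. An A3 patient who has a given preferred term in Weeks 0-8 is counted as a case on 150 mg time and adds no time on 300 mg for that term. Both effects move the A3/A2 ratio toward 1, so a real dose-related excess after Week 8 would look smaller in the only exposure-adjusted table that covers those weeks for Group A.

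**Working it through.** **Planned clock.** SAP 2.1.1 gives 8 weeks on treatment in Period 1 and 16 in Period 2: 8 + 16 = 24, which matches its stated 24-week treatment phase. In days, the first dose is Day 1, Week 8 is Day 57 (SAP Table 2-1) and Week 24 is 24 × 7 + 1 = Day 169. For an event-free completer:
- Group A arms: 169 − 1 + 1 = 169 days, of which 56 precede re-randomisation (56/169 = 33%).
- Group B arms: 169 − 57 + 1 = 113 days, none before re-randomisation.

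SAP Table 2-1 lists Week 24 as Day 162. On that day count the clocks are 162 and 106 days, and the share is 56/162 = 35%.

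**Dilution when events are rare.** Let the A2 rate after Week 8 be 1, the A3 rate after Week 8 be R, and the common rate in Weeks 0-8 be k. Then

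apparent A3/A2 = (8k + 16R) / (8k + 16).

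With k = 1: R = 1.5 gives 32/24 = 1.33; R = 2 gives 40/24 = 1.67; R = 3 gives 56/24 = 2.33.

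**Adding the stop at first event.** With constant yearly hazards h1 (first 56 days) and h2 (next 113 days), S1 = exp(−h1 × 56/365.25) and S2 = exp(−h2 × 113/365.25), the expected rate is

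(1 − S1·S2) / [(1 − S1)/h1 + S1·(1 − S2)/h2].

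Example: h1 = 0.5 in both arms, h2 = 0.5 in A2 and 1.0 in A3. The A2 rate is 0.5. For A3, S1 = 0.9262 and S2 = 0.7339, so the rate is 0.3203 / (0.1476 + 0.2465) = 0.813, and the ratio to A2 is 1.625.

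The documents give no AE hazards, so the table shows a range. Entries are the apparent A3/A2 ratio.

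| A2 hazard after Week 8 (per year) | Weeks 0-8 rate ÷ later A2 rate | True 1.5 | True 2 | True 3 |
|---|---|---|---|---|
| 0.1 | 1 | 1.331 | 1.660 | 2.313 |
| 0.5 | 1 | 1.317 | 1.625 | 2.217 |
| 1.5 | 1 | 1.282 | 1.539 | 1.984 |
| 0.1 | 2 | 1.248 | 1.495 | 1.984 |
| 0.5 | 2 | 1.235 | 1.464 | 1.902 |
| 1.5 | 2 | 1.203 | 1.389 | 1.709 |

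**B1 versus B2.** The clock has one segment, from the Week 8 dose, so a true ratio of 2 shows as 2.0 in every row.

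**If columns are pooled by Period 2 dose.** Assume 264/88 recruited, 43.6% response, no drop-out and equal re-randomisation (the text gives no ratio). Then A3 has 264 × 0.564/2 = 74.4 patients and B2 has 44. The share of the 300 mg clock that is really 150 mg time is 74.4 × 56 / (74.4 × 169 + 44 × 113) = 24%.

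**Numerator and clock do not match.** Treatment-emergent events count from the first dose of study treatment, and SAP 2.1.1 includes placebo in that term. Read literally, a Group B event on Day 20 has an entire-period duration of 20 − 57 + 1 = −36 days.

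**With the clock at the Week 8 dose.** All five arms have 113 planned days, and A3/A2 recovers the assumed ratio.

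**The case against.** The strongest reply is that the stated endpoint is already served. SAP Table 1.2-1 asks for frequency and severity, not an exposure-adjusted rate. SAP 2.8 and 2.1 give crude Period 2 summaries by the five arms, with the same planned 16 weeks in each, so A2 can be set against A3 there without Weeks 0-8. The exposure-adjusted table is an addition, and the objective is exploratory. All of this stands. A reader might infer that nothing at all is planned for Weeks 8-24 alone; the documents do not support that. What is missing is an exposure-adjusted rate, which is the display meant to handle unequal time at risk when patients stop early.

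Second, the SAP does not state the columns of the entire-period tables. Dropping placebo time fits a pooled any-secukinumab display just as well, and in that layout there is no A3/A2 ratio to dilute. This also stands, so the point is conditional on display by arm or by dose.

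Third, the general sentence in SAP 2.8, that safety analyses are done for each period, could be read as covering exposure-adjusted rates too. The specific text in 2.8.1 names the entire period and supplies no Period 2 duration, so a programmer would have no rule to apply.

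**Conclusion.** The point holds for A3 versus A2. If the entire-period exposure-adjusted rates are shown by arm or by dose, a third of planned A2 and A3 time precedes the randomised dose difference. With equal early and late rates, a true ratio of 2 shows as about 1.67 at most, and as 1.54 to 1.66 over the assumed hazards of 0.1 to 1.5 per year. If the early rate is twice the later one, it shows as 1.39 to 1.50. The dilution itself needs no change of rate over time; only its size depends on the assumed hazards.

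Two stronger readings are tempting and should not be drawn. One is that every exposure-adjusted dose comparison is affected. It is not: the B1 and B2 clock already starts at Week 8, so by arm that comparison is clean. The other is that Group A and Group B arms must differ because Group A's clock includes the weeks with more frequent visits. With a constant rate the A2/B1 ratio is 1.00. It departs from 1 only if event or recording rates change over time (1.34 to 1.44 if the early rate is doubled). Protocol 7.1 also accepts AEs volunteered between visits, so visit frequency is not a measure of recording rate. A versus B is not among the listed arm contrasts, and Arms A1 to A3 are split by Week 8 response in any case.

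This concerns supplementary safety tables, not the primary analysis. It is a cheap improvement worth making.

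**What to change.** In SAP 2.8.1, and by reference in 2.8.1.1:
- Add a Treatment Period 2 exposure-adjusted rule for all five arms. Start the clock at the Week 8 dose and count only events that start or worsen after it. Use it for A2 versus A3 and B1 versus B2.
- State the columns of the entire-period table and limit it to a pooled any-secukinumab summary, counting only events that start or worsen after the first active dose. This also removes the negative durations.

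The cost is SAP wording and one more run of an existing table. The downside is fewer events per cell and wider intervals in the Period 2 table.

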2.1.1 General definitions

Study treatment: Study treatment refers to:

Secukinumab 150 mg provided in 1 ml PFS or secukinumab placebo provided in 1 ml PFS.

Study treatment start and end date: Study treatment start date is defined as the first date, when a non-zero dose of study drug is administered and recorded on the Drug Administration Record (DAR) CRF page. Similarly, study drug end date is defined as the last date, when a non-zero dose of study drug is administered and recorded on the DAR CRF page of the core study.

Study day: Study day will be calculated as (event date – study drug start date + 1 day) for events that occurred on or after study drug start date (e.g., visit, lab samples, AEs). For events prior to study drug start date (e.g., time of diagnosis), study day will be negative and calculated as (event date – study drug start date). Note that study drug start date is study day 1 and the day before study drug start date is study day -1 (i.e. no study day 0).

Due to the study drug dosing schedule, one month will be considered as 28 days. However, for “time since event” data (e.g., medical history), one month will be considered as 365.25/12 days for events that occurred prior to study Day 1. Time from events prior to the start of study drug, e.g., time since diagnosis, is calculated as the difference between the start date of study drug and the date of prior event.

Note that, the first dose day is Day 1, and the day before the first dose day is counted as Day - 1 (not Day 0).

Baseline and post baseline: In general, a *baseline* value refers to the last measurement made prior to administration of the first dose of study treatment. A post-baseline value refers to a measurement taken after the first dose of study treatment.

Treatment Period: There are 2 treatment periods for this study defined as:

Treatment Period 1 is defined as an 8-week placebo-controlled, double-blind treatment period starting from baseline till Week 8. Assessments of Week 8 are included in TP1 whereas administration of study drug at week 8 will be a part of TP2. Week 8 is the last visit of TP1 for all assessments except drug intake.

Treatment Period 2 is a 16 week double-blinded, active treatment period starting from Week 8 till Week 24 for administration of study drug. Week 8 assessments are considered as the baseline values for assessments during TP2.

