2.2 Analysis sets

The following analysis sets will be used in this study:

The **Enrolled Set** will include all patients, who provided informed consent.

The **Randomized Set** will consist of all patients, who were randomized into this study at Baseline. Mis-randomized patients will not be included in this analysis set.

[figure not shown]
The **Safety Set for Treatment Period 1 (SAF-TP1)** will consist of all patients, who received at least 1 dose of study treatment during this treatment period. Data will be analyzed according to the treatment actually received.

The **Safety Set for Treatment Period 2 (SAF-TP2)** will consist of all patients, who received at least 1 dose of study treatment during this treatment period. Data will be analyzed according to the treatment actually received.

The **Safety set (SAF)** will consist of all patients, who received at least one dose of study treatment. To analyze entire study period safety assessments, this dataset will be used.

The **Full Analysis Set for Treatment Period 1 (FAS-TP1)** will consist of all patients, who were randomized into this study at Baseline and received at least 1 dose of study treatment during this treatment period. Data will be analyzed according to the treatment assigned at randomization.

The **Full Analysis Set for Treatment Period 2 (FAS-TP2)** will consist of all patients, who were re-randomized or re-assigned at Visit 7 (Week 8) and received at least 1 dose of study treatment during this treatment period. Data will be analyzed according to the treatment assigned at randomization.

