Above AESI will be considered and the number of patients with at least one event in each AESI grouping will be reported. Such AESI grouping consist of adverse events, for which there is a specific clinical interest in connection with secukinumab, or adverse events, which are similar in nature (although not identical).

All AESI groupings are defined through the use of PT, high level terms (HLT), SOC, SMQ, NMQ or through a combination of these components.

The AESI search table will be used to map reported adverse events to the notable adverse events groupings. The list of adverse events of special interest may be updated during the course of the trial based on accumulating safety data. Therefore, the clinical study report will list the AE groupings used and provide a listing of the corresponding AESI search table.

The crude rates of adverse events of special interest will be summarized by primary system organ class and preferred term.

In addition, exposure time-adjusted incidence rates including 95% confidence intervals will be provided for the entire treatment period at the preferred term level to adjust for differences in exposure. A graphical display of the crude rates and exposure-adjusted incidence rates will be presented for all AESIs by SOC.

Note that certain adverse events may be reported within multiple groupings.

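### SAP 2.8.1 removes placebo time from the entire-period exposure-adjusted AE rates but has no matching rule for placebo-phase events, so a Group B event before the first active dose is counted with zero or negative days

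*SAP*

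**What the plan says.** SAP 2.8.1 defines the exposure-adjusted rate as "Number of patients with new or worsened treatment emergent AEs" divided by total time on treatment in years. It gives one duration rule for Treatment Period 1 reports and another for entire-period reports. The entire-period rule has this instruction:

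- "Please do not consider the duration when the subject is on placebo"

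For a patient with an event it then gives:

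- "If event occurred till week x: Duration=AE start date- date of first dose on active study treatment +1"

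A patient without an event contributes time from the same starting date to the date of week x.

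Three other definitions feed into the rate:

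- **Treatment-emergent (2.8.1):** includes "events that started after the first dose of study treatment".
- **Study treatment (2.1.1):** "Secukinumab 150 mg provided in 1 ml PFS or secukinumab placebo provided in 1 ml PFS".
- **Population (2.2):** the Safety Set is all patients "who received at least one dose of study treatment. To analyze entire study period safety assessments, this dataset will be used".

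The entire-period rates, with 95% confidence intervals, are planned for all SAEs and common AEs in 2.8.1. In 2.8.1.1 they are planned for AEs of special interest "for the entire treatment period at the preferred term level to adjust for differences in exposure". Both sections add graphical displays by system organ class.

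**The concern.** The denominator and the numerator cover different periods. Group B receives only placebo until Week 8. The duration rule takes those weeks out of the person-time, but no sentence in SAP 2.8, 2.8.1 or 2.8.1.1 takes the events of those weeks out of the count.

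Read literally, the rule does two things to a Group B patient whose first event of a given term falls in the placebo phase. It counts the patient as an event against active-drug time, and it gives that patient a duration that is zero or negative. A Group B patient who stopped before Week 8 is in the Safety Set but has no first active dose from which to compute a duration.

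At stake is the planned exposure adjustment for SAEs, common AEs and AEs of special interest. Events that occurred on placebo could be reported as part of a rate on secukinumab.

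**Working it through.** **Inputs from the documents**

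- Week 8 is the planned first active dose for Group B (SAP 1.1). Its scheduled day is 57 (SAP Table 2-1), which reproduces as 7 x 8 + 1 = 57.
- Planned sizes are 264 in Group A and 88 in Group B (SAP 1.1).
- Week 24 is printed as Day 162 in SAP Table 2-1, while 7 x 24 + 1 = 169. Both cut-offs are used below.

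**Step 1: the duration rule.** Duration = AE day - first active dose day + 1.

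| Group B AE onset | First active dose Day 57 | Duration (days) |
|---|---|---|
| Day 20 | 20 - 57 + 1 | -36 |
| Day 55 | 55 - 57 + 1 | -1 |
| Day 56 | 56 - 57 + 1 | 0 |
| Day 57 | 57 - 57 + 1 | 1 |

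The zero point moves with the actual dose date: it is Day 54 if dosing is on Day 55, and Day 58 if dosing is on Day 59. In Group A the first dose is already active, so the rule gives at least 1 day. For 88 patients, the placebo time removed is 88 x 56 / 365.25 = 13.5 patient-years.

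**Step 2: one affected term (assumed counts).** Of 88 Group B patients, 2 have the term on placebo (mean Day 28, so -28 days each). Another 4 have it first on active drug (mean 56 active days). The other 82 have no event and contribute 169 - 57 + 1 = 113 days each.

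- As written: (2 x -28 + 4 x 56 + 82 x 113) / 365.25 = 25.83 patient-years; 6 / 25.83 = 23.2 per 100 patient-years.
- Active-phase events only: (4 x 56 + 84 x 113) / 365.25 = 26.60 patient-years; 4 / 26.60 = 15.0 per 100 patient-years.
- Ratio: 1.54. The numerator contributes 6 / 4 = 1.50 and the denominator 26.60 / 25.83 = 1.03.

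**Step 3: expectation over all terms.** Assumptions:

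- The active-phase rate per term is constant, at 0.05, 0.20 or 0.50 per patient-year.
- The placebo-phase rate is a stated fraction of the active rate.
- Follow-up is complete, and the daily first-event probability is 1 - exp(-rate / 365.25).
- Events with non-positive duration are kept.

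The documents give no placebo-to-active rate ratio per term. Protocol 3.7 says only that total AEs were more frequent on secukinumab, so a range is shown. Each entry is the reported rate divided by the true active rate, over the three rates and both cut-offs.

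| Placebo rate / active rate | Group B | Pooled 264 + 88 |
|---|---|---|
| 1.00 | 1.50 to 1.63 | 1.09 to 1.11 |
| 0.75 | 1.38 to 1.46 | 1.07 to 1.08 |
| 0.50 | 1.25 to 1.30 | 1.05 |
| 0.25 | 1.13 to 1.15 | 1.02 to 1.03 |

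Group A stays at 1.00. The SAP does not define columns for the entire period, so the pooled column is an illustration.

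**Step 4: other handling of the same events.** At equal rates, setting non-positive durations to zero while keeping the events gives 1.50 to 1.59 in Group B. Dropping the events together with their durations gives 1.00 in every scenario.

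**Step 5: how often a term is touched.** The share of Group B with a placebo-phase event is 1 - exp(-fraction x rate x 56 / 365.25). The chance that at least one of 88 has one is 1 - (1 - share)^88.

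| Active rate per patient-year | Equal rates | Placebo half of active |
|---|---|---|
| 0.01 | 13% | 7% |
| 0.05 | 49% | 29% |
| 0.20 | 93% | 74% |

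**The case against.** The best defence is that the intent is evident. The entire-period rule is explicitly about active treatment, and SAP 2.4.1 says "Compliance for entire treatment period will be based on active treatment exposure". Placebo-phase AEs are reported in the Treatment Period 1 summaries anyway. A negative or missing duration would probably show up in routine programming checks, and if those events are then dropped there is no bias.

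Much of this stands, and it limits the point. A reader might infer that the reported rates will be inflated, or that the authors chose to charge placebo events to active drug. The documents support neither inference: they show a rule that fails as written and do not say what would be done on discovering it. That silence is why the defence does not remove the point. The instruction on placebo speaks only of duration. A programmer who notices the problem must choose between dropping the event, dropping the patient, setting the time to zero or looking for a later event, and Step 4 shows that the choice changes the rate.

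Four other tempting readings also go too far:

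- **Negative days as the main harm.** Setting them to zero leaves almost the same inflation. The retained numerator is the main cause.
- **The denominator always falls.** It need not when the event is in a patient who never received active drug, because that patient has no active days to lose.
- **The multipliers in Step 3 as the error in each affected term.** They are averages over all terms, including untouched ones. A single affected term depends on its own counts, as Step 2 shows.
- **A mismatch in the cut-off.** Both branches of the duration rule already use the same week x. Its unstated value is a separate matter.

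**Conclusion.** The rule in SAP 2.8.1 is wrong as written for entire-period exposure-adjusted rates: placebo time is excluded and placebo-phase events are not. It should be corrected, but it is a limited defect.

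If the events are kept, the rate is overstated for Group B preferred terms with a placebo-phase event, and for the system organ class and special-interest displays built on the same rule. The expected overstatement, averaged over terms, is about 1.1-fold to 1.6-fold in Group B and 1.02-fold to 1.11-fold if the groups are pooled. These sizes rest on the assumed rates, constant hazards, complete follow-up and retention of the events. Many rare SAE terms would not change at all.

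The rates are descriptive. Crude rates, Treatment Period 1 rates, Group A and all efficacy analyses are unaffected.

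**What to change.** Add to the entire-period rule in SAP 2.8.1, and apply it to 2.8.1.1:

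- For each preferred term or grouping, count only a patient's first AE that starts or worsens on or after the first active dose.
- Include only patients who received at least one active dose.

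Placebo-phase events stay in the Treatment Period 1 summaries. With this rule the shortest possible duration is 1 day, and the Step 3 calculation returns 1.00 for Group B at every placebo rate. The cost is one or two sentences of SAP text and a few lines of programming, with no new data.
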